### **7.5.2.9 Secondary Efficacy Endpoints**

#### **Overall Survival in CPS $\geq 1$ subjects and All Randomized Subjects**

If the OS primary endpoint in randomized CPS  $\geq 5$  subjects is significantly superior then OS in randomized CPS  $\geq 1$  subjects will be compared using a two-sided log rank test and a significance level of 1.5%, stratified by the stratification factors as specified in [Table 7.5-1](#). Similarly if OS testing in randomized CPS  $\geq 1$  subjects is significantly superior then OS in all randomized subjects (all comers) will be compared using a two-sided log rank test and a significance level of 1.5%, stratified by the stratification factors as specified in [Table 7.5-1](#).

The stratified hazard ratio between the treatment groups will be presented along with 100\* (1 -  $\alpha$ )% CI (adjusted for interim). In addition, two-sided p-value will also be reported for the analysis of OS.

OS will be estimated using the KM techniques. A two-sided 95% CI for median OS in each treatment group will be computed via the log-log transformation method. OS rates at fixed time points (eg, 6, 12, 18, 24 months, depending on the minimum follow-up) will be presented along with their associated 95% CIs. These estimates will be derived from the Kaplan Meier estimate and corresponding CIs will be derived based on Greenwood formula for variance derivation and on log-log transformation applied on the survivor function.

#### **Additional Analyses for OS in CPS $\geq 1$ subjects and All Randomized Subjects**

As OS in CPS  $\geq 1$  subjects and OS in all randomized subjects are tested hierarchically, the following analyses will only be conducted if the endpoint is statistically significant:

All analyses as described in [Sections 7.5.2.5, 7.5.2.6 and 7.5.2.8](#).

#### **Overall Survival in CPS $\geq 10$ subjects**

This endpoint will not be formally tested. The stratified hazard ratio between the treatment groups will be presented along with 95% CI. OS will be estimated using the KM techniques. A two-sided 95% CI for median OS in each treatment group will be computed via the log-log transformation method. OS rates at fixed time points (eg, 6, 12, 18, 24 months, depending on the minimum follow-up) will be presented along with their associated 95% CIs. These estimates will be derived from the Kaplan Meier estimate and corresponding CIs will be derived based on Greenwood formula for variance derivation and on log-log transformation applied on the survivor function.

**PFS (BICR) in CPS ≥ 10, 1 and in all randomized:**

These endpoints will not be formally tested. PFS using primary definition per BICR will be analyzed. The stratified HR with its associated two-sided 95% CI will be estimated via a stratified Cox model with treatment arm as the only covariate in the model. PFS will be estimated using the KM techniques. A two-sided 95% CI for median PFS in each treatment group will be computed via the log-log transformation method. PFS rates at fixed time points (eg, 6, 12, 18 months, depending on the minimum follow-up) will be presented along with their associated 95% CIs. These estimates will be derived from the Kaplan Meier estimate and corresponding CIs will be derived based on Greenwood formula for variance derivation and on log-log transformation applied on the survivor function.

**Best Overall Response and ORR (BICR) in CPS ≥ 10, 5, 1 and in all Randomized Subjects**

These endpoints will not be formally tested. The analyses will be repeated for the 4 populations: CPS ≥ 10, CPS ≥ 5, CPS ≥ 1 and all randomized. The analyses using BICR data are considered as secondary endpoints (no formal testing). The analyses will be repeated on subjects with measurable disease at baseline (see Section 6.3)

- The number and percentage of subjects in each category of BOR (complete response [CR], partial response [PR], stable disease [SD], progressive disease [PD], or unable to determine [UTD]) will be presented, by treatment group.
- Estimates of response rate, along with its exact two-sided 95% CI by Clopper and Pearson will be presented, by treatment group.
- A 2-sided, 95% CI for the difference of ORR between treatment groups will also be computed by the method of DerSimonian and Laird, using a fixed-effects model (setting Δ2 equal to zero), adjusting for the stratification factors. The weighted response rate difference and 95% CI can be determined using the following formula:

$$\hat{\theta} = \frac{\sum_{i=1}^{24} \hat{\theta}_i w_i}{\sum_{i=1}^{24} w_i} \sim N(\theta, 1 / \sum_{i=1}^{24} w_i)$$

where  $\hat{\theta}_i$  is the response rate difference of the  $i^{\text{th}}$  stratum and  $w_i = 1/\text{var}(\hat{\theta}_i)$ .

- In addition, the stratified (source: IVRS) odds ratios (Mantel-Haenszel estimator) between the treatments will be provided along with the 95% CI.
- ORR based on BICR assessment per RECIST 1.1 will be compared between two treatment groups using a two-sided Cochran-Mantel-Haenszel (CMH) test, stratified by the stratification factors. This p-value is descriptive only.

The following subject-level graphics will also be provided:

- For the responders only, time courses of the following events of interest will be graphically displayed: tumor response, progression, last dose received, and death.
- For response evaluable subjects (randomized subjects with evaluable\* baseline and at least one evaluable\* on-study tumor assessment),

- A bar plot showing the best % reduction from baseline in sum of diameter of target lesions based on BICR assessment for each subject will be produced (excluding assessments after PD and assessments after start of subsequent anti-cancer therapy).
- A plot of individual time course of tumor burden change per BICR assessment will be produced.

\*Evaluable is defined according to RECIST v1.1

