ORR (as assessed by BICR and as assessed by investigator) and DRR (as assessed by BICR and as assessed by investigator) will be computed in each treatment group along with the exact 95% CI using Clopper-Pearson method. ⁹⁴ An estimate of the difference in ORRs and DRRs, and corresponding 95% CI will be calculated using Cochran-Mantel-Haenszel methodology and adjusted by the randomization stratification factors. The stratified odds ratios (Mantel-Haenszel estimator) between the treatments will be provided along with the 95% CI.

Duration of Response (as assessed by BICR and as assessed by investigator) in each treatment group will be estimated using KM product-limit method for subjects who achieve PR or CR. Median values along with two-sided 95% CI will be calculated.

Survival rate analysis will be carried out only for those time points which are mature enough by the time of the given database-lock. Point estimates will be provided using KM product-limit method. For each survival rate per treatment arm, two-sided 95% CIs using log-log transformation will be computed.

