Assess impact of Potential Prognostic Factors on Treatment Effect:

- 3) A multivariate Cox regression model will be used in order to estimate the treatment effect after adjustment for possible imbalances in known or potential prognostic factors. The factors used in the randomization, will be included in the model as stratification factors. However, all additional factors will be incorporated as covariates. The additional factors, which are all measured at baseline, will include:
- Age categorization ( $< 65$ ,  $\geq 65$ )
  - Gender (Male vs. Female)
  - Primary tumor location at initial diagnosis (GC, GEJ cancer, Esophageal Adenocarcinoma)
  - Disease status (locally recurrent/advanced, metastatic)
  - Lauren classification (intestinal type, diffuse type, mixed, unknown)
  - Peritoneal metastases (yes/no)
  - Prior surgery related to current cancer OR radiotherapy finished more than 6 months before randomization (yes/no)
  - Number of organs with baseline lesion (target or non-target;  $\leq 1$ ,  $\geq 2$ ) outside primary location (gastric, gastroesophageal junction and esophagus)
  - WHO histologic classification presence of signet ring cell (yes/no)

The level of the covariate normally associated with the worst prognosis will be coded as the reference level. The hazard ratio associated with treatment and with each of the baseline covariates will be presented along with associated 95% CIs.

- 4) The identification of the primary population using PD-L1 CPS  $\geq 5$  was introduced close to accrual completion. Therefore the randomization was not stratified by PD-L1 CPS  $\geq 5$ . The overall study population was stratified by
- PD-L1 expression level (tumor cells) ( $\geq 1\%$  vs.  $< 1\%$  or indeterminate)
  - Region: Asia vs. US vs. RoW
  - ECOG performance status: 0 vs. 1
  - Planned chemotherapy regimen (XELOX vs. FOLFOX)

As CPS $\geq 5$  is not a stratification factor, while pronounced imbalance is not expected due to the large sample size in this group, thorough review of data will be conducted and a sensitivity analysis may be conducted.

The distribution of baseline characteristics (demographics, disease characteristics and the stratification factors) between the two treatment arms will be inspected for potential imbalance in the subgroup of subjects with PD-L1 CPS  $\geq 5$ .

The distribution of these characteristics will also be assessed between the CPS PD-L1  $\geq 5$  subgroup and the overall population, regardless of treatment.

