##### **ORR (investigator) in CPS $\geq 10$ , 5, 1 and in all randomized subjects:**

Similar analyses than for Best Overall Response and ORR per BICR will be produced but using investigator assessment of response and progression.

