### **Durable response rate (BICR and investigator) in all randomized CPS $\geq 5$ subjects**

Durable response will be evaluated per BICR assessment and per investigator assessment for subjects with measurable disease at baseline. The durable response rate will be computed in each treatment group along with the exact 95% CI using Clopper-Pearson method. An estimate of the difference in DRRs and corresponding 95% CI will be calculated using DerSimonian and Laird methodology and adjusted by the stratification factors as specified in [Table 7.5-1](#). The stratified odds ratios (Mantel-Haenszel estimator) between the treatments will be provided along with the 95% CI.

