### **ORR (investigator) in CPS $\geq$ 10, 5, 1 and in all randomized subjects:**

Similar analyses than for Best Overall Response and ORR per BICR will be produced but using investigator assessment of response and progression.

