### **Durable response rate (BICR) in CPS $\geq$ 5 and all randomized subjects**

Durable response will be evaluated per BICR assessment and per investigator assessment for subjects with measurable disease at baseline. The durable response rate will be computed in each treatment group along with the exact 95% CI using Clopper-Pearson method. An estimate of the difference in DRRs and corresponding 95% CI will be calculated using CMH methodology and adjusted by the stratification factors as specified in [Table 7.5-1](#). The stratified odds ratios (Mantel-Haenszel estimator) between the treatments will be provided along with the 95% CI.

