### **8.1.2 ORR and DOR**

For ORR and DOR as assessed by BICR, ORR will be computed in each of the 3 treatment groups along with the exact 95% CI using Clopper-Pearson method. An estimate of the difference in ORRs and corresponding 95% CI between each pair of treatment arms will be calculated using CMH methodology and adjusted by the stratification factors as specified in [Section 7.1.1](#). The stratified odds ratios (Mantel-Haenszel estimator) between each pair of treatment arms will be provided along with the 95% CI. DOR for each of 3 treatment groups will be estimated and overlaid using KM product limit method for subjects who achieve PR or CR. Median values along with two-sided 95% CI will be calculated.

These analyses will be produced for

- All concurrently randomized subjects to the 3 arms with measurable disease (BICR)
- All concurrently randomized subjects to the 3 arms with measurable disease (BICR) and PD-L1 CPS  $\geq 5$
- All concurrently randomized subjects to the 3 arms with measurable disease (BICR) and with PD-L1 CPS < 5.
- All randomized subjects to the 3 arms with measurable disease (BICR)
- All randomized subjects to the 3 arms with measurable disease (BICR) and PD-L1 CPS  $\geq 5$
- All randomized subjects to the 3 arms with measurable disease (BICR) and PD-L1 CPS < 5.

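### The SAP replaces the protocol's CMH method for the ORR and N+C DRR differences with inverse-variance weights that can be undefined and whose nominal 95% CI under-covers

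*SAP*

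**What the plan says.** Protocol 8.4.2.3 covers ORR and DRR, each by BICR and by investigator. For the difference in either rate, the estimate and "corresponding 95% CI will be calculated using Cochran-Mantel-Haenszel methodology and adjusted by the randomization stratification factors".

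The SAP is not uniform:

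- **ORR by BICR, N+C (7.5.2.9) and N+I (7.5.3.8).** A 95% CI for "the difference of ORR between treatment groups will also be computed by the method of DerSimonian and Laird", with the between-stratum variance set to zero. The printed formula weights each stratum difference by the reciprocal of its variance and sums over 24 strata (N+C) or 12 strata (N+I).
- **DRR, N+C (7.5.2.10).** The difference "will be calculated using DerSimonian and Laird methodology and adjusted by the stratification factors".
- **DRR, N+I (7.5.3.9).** The difference is "calculated using CMH methodology and adjusted by the stratification factors".
- **ORR, contribution of components (8.1.2).** The difference "between each pair of treatment arms will be calculated using CMH methodology and adjusted by the stratification factors".
- **ORR by investigator (7.5.2.10 and 7.5.3.9).** "Similar analyses than for Best Overall Response and ORR per BICR will be produced", so it inherits the inverse-variance method.

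For ORR, 7.5.2.9 and 7.5.3.8 also give a Mantel-Haenszel odds ratio, a descriptive CMH p-value and exact CIs per arm. Only the difference and its CI depart from the protocol. Neither these sections nor the document history (Table 11-1) mentions the departure or explains it.

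**The concern.** There are three problems.

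1. **Inconsistency.** The SAP departs from the protocol without saying so. It also uses two methods for the same endpoint: DRR is inverse-variance for N+C and CMH for N+I.
2. **Incomplete formula.** The weight is one over the stratum variance. If each arm of a stratum has 0% or 100% response, that variance is zero and the weight is undefined. No repair is stated, so two programmers could report different results from the same data.
3. **Under-coverage.** The weights are computed from the same responses as the differences they weight. This makes the estimate slightly biased, adds variability that the standard error ignores, and makes the standard error slightly small.

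BICR ORR is a listed secondary endpoint (SAP 3.2 and 4.2.1.3). Because it is not formally tested, the difference and CI are a main part of its comparative result. They are reported in four populations per comparison and repeated in subjects with measurable disease. The smallest of the four, CPS ≥ 10, is where the loss is greatest.

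**Working it through.** **Reproducing the plan's figures.** Region has 3 levels; ECOG, TPS and chemotherapy regimen have 2 each. So 3×2×2×2 = 24 strata for N+C and 3×2×2 = 12 for N+I, as the SAP states. The sizes also reproduce: 1582×0.60 = 949 and 815×0.60 = 489 (SAP 5.1 and Appendix 5).

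**Estimators compared.**
- SAP: θᵢ = p₁ᵢ − p₀ᵢ, wᵢ = 1/[p₁ᵢ(1−p₁ᵢ)/n₁ᵢ + p₀ᵢ(1−p₀ᵢ)/n₀ᵢ], estimate Σwᵢθᵢ/Σwᵢ, SE = 1/√Σwᵢ.
- Comparator: Mantel-Haenszel risk difference with Sato or Greenland-Robins variance.

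**Assumptions, because the documents do not give stratum sizes or final rates.** The documents report chemotherapy ORR of 30-50% (Protocol 1.1.1), N+C 60-70% (1.1.5.1) and N+I 26% (1.1.3). The main rates used were 60% v 45% for N+C and 30% v 45% for N+I. DRR was taken as 35% v 20%. There were three stratum mixes:
- (a) equal strata;
- (b) region 25/15/60% with TPS ≥ 1% in 16%;
- (c) region 25/8/67% with TPS ≥ 1% in 15%.

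Mixes (b) and (c) take ECOG 0 as 42% and XELOX as 50% (N+C only). The smallest expected stratum at N=949 is then:
- (a) 949/24 = 39.5;
- (b) 949×0.15×0.16×0.42×0.50 = 4.8;
- (c) 949×0.08×0.15×0.42×0.50 = 2.4.

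Each setting used 40,000 simulated trials, with a constant risk difference and the same rates in every stratum.

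**Undefined weights.** In a stratum with two subjects per arm at 60% v 45%, the chance that both arms are all-or-none is (0.6²+0.4²)×(0.45²+0.55²) = 0.52×0.505 = 0.26. Over the three mixes at N=949, at least one zero-variance stratum occurs in 0% (equal strata) to about 90% of trials.

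**Under-coverage with no undefined weight (N=949, equal strata).** The correct SE is √{[(0.60×0.40 + 0.45×0.55)/(39.5/2)]/24} = 3.2 points. Mantel-Haenszel matches this, with SD 3.2 and SE 3.2. The SAP formula has true SD 3.4, mean SE 3.1 and bias +0.8. A normal approximation shows the effect:
- Half-width: 1.96×3.1 = 6.08.
- Coverage: Φ((6.08−0.8)/3.4) − Φ((−6.08−0.8)/3.4) = Φ(1.55) − Φ(−2.02) ≈ 91.8%. Simulated: 91.7%.
- Bias removed: 2Φ(6.08/3.4) − 1 ≈ 92.6%. Simulated: 92.7%.

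Most of the shortfall therefore comes from the standard error and the random weights. The bias arises at these rates because a stratum with a high observed N+C rate or a low observed control rate has a smaller estimated variance and so gets more weight.

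**Coverage of the nominal 95% CI, zero-variance strata dropped:**

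| Comparison, assumed rates | N | Near 1:1 in strata | Allocation not forced 1:1 |
|---|---|---|---|
| N+C ORR, 60% v 45% | 1582 | about 93% | – |
| N+C ORR, 60% v 45% | 949 | 91-92% | 88-91% |
| N+C ORR, 50% v 40% | 949 | about 92% | 88-92% |
| N+I ORR, 30% v 45% | 815 | 93-94% | – |
| N+I ORR, 30% v 45% | 489 | about 92% | 89-92% |
| N+C DRR, 35% v 20% | 949 | about 93% | 90-92% |
| N+C DRR, 35% v 20% (80% measurable) | 759 | about 92% | 89-90% |
| N+C ORR, CPS ≥ 10 (assumed size) | 475-790 | 86-91% | 80-90% |
| N+I ORR, CPS ≥ 10 (assumed size) | 245-408 | 88-92% | 84-91% |

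The last column is left blank for all randomized subjects because the analysis strata were randomization strata there. It is relevant to the CPS subsets: "Therefore the randomization was not stratified by PD-L1 CPS" ≥ 5 (SAP 7.5.2.2).

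**Other repairs and the comparator.**
- Adding 0.5 to every cell gives 93-94% at N=949 (60% v 45%). It changes the N+C ORR bias from between +0.4 and +0.9 points to between −0.2 and 0 (outside CPS ≥ 10).
- Mantel-Haenszel with Sato variance gives 94.6-95.2% in every setting, with bias near 0.
- Mantel-Haenszel with Greenland-Robins variance gives 94.0-94.8% outside CPS ≥ 10 and 93.3-94.4% in it.

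**The case against.** The strongest reply concerns importance. ORR and DRR are not formally tested, DRR is exploratory, and the bias outside CPS ≥ 10 is under 1 point. The corrected interval at N=949 widens only from 12.2 to 12.6 points. The CMH p-value, Mantel-Haenszel odds ratio and exact per-arm CIs are retained, and no conclusion has been shown to change. This is correct, and it limits the severity. It does not repair the difference and CI, which are reported as nominal 95% results.

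A second reply is that the larger shortfalls depend on dropping zero-variance strata and on assumed mixes. That is partly right: with 0.5 added to every cell, the shortfall at N=949 is about 1 to 2 points. But coverage was below 95% under each repair, including with equal strata, where no weight is undefined. The CPS ≥ 10 figures have the weakest basis, because size, mix and rates are all assumed. They support the direction only.

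A third is that the protocol names no variance estimator, so the 95% result with Sato goes beyond its text. This stands, and the estimator must be chosen explicitly. Finally, nothing in the document history suggests a data-driven change of method, and none is alleged.

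**Conclusion.** The concern holds. The SAP contradicts the protocol for the ORR difference in both comparisons and for the N+C DRR difference. It is inconsistent with itself and has no rule for an undefined weight. These points rest on the text alone.

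The size of the under-coverage rests on assumed response rates and stratum mixes. With zero-variance strata dropped and near-1:1 allocation, the shortfall is about 1 to 2 points in all randomized subjects. For ORR it is about 3 to 4 points at N=949 and about 3 points at N=489. It is larger in smaller subsets. The direction was the same in every setting tried. Type I error control and the primary conclusions are unaffected. The point should be corrected, but it does not threaten the trial's main results.

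**What to change.** Use the Mantel-Haenszel weighted risk difference, as the protocol intends, in SAP 7.5.2.9, 7.5.3.8 and the N+C DRR paragraph of 7.5.2.10. The investigator-assessed ORR analyses that refer to these sections will then follow. Name a variance estimator that is valid with sparse strata; Sato is one option.

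SAP version 5.0 was written after the N+C PFS and interim OS analysis and its study report (Table 11-1). For N+C results already reported, show the Mantel-Haenszel difference and CI beside them, labelled as a re-run after unblinding.

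If the inverse-variance method is kept, state that it departs from the protocol, why, and how zero-variance strata are handled.

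The cost is SAP wording, a standard procedure option and a small N+C re-analysis, with no new data. The CI becomes about 3% wider: 12.2 to 12.6 points at N=949 (12.6/12.2 = 1.03) and 16.4 to 16.9 points at N=489 (16.9/16.4 = 1.03).

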### **Subset Analyses of Objective Response**

The influence of baseline and demographic characteristics on the treatment effect will be explored via exploratory subset analysis. BICR assessment of ORR in CPS  $\geq 5$  subjects will be summarized for the same subgroups than for PFS (see [Section 7.5.2.3](#)).

A forest plot of treatment effect on ORR per BICR in CPS  $\geq 5$  subjects will be produced. The un-weighted differences in ORR between the two treatment groups and corresponding 95% two-sided CI using the method of Newcombe will be provided. The analysis comparing treatment (ie, ORR difference) will be conducted if the number of subjects in the subgroup category is more than 10.

#### ***7.5.2.10 Exploratory Efficacy Endpoints***

##### **PFS (investigator) in CPS $\geq 10$ , 5, 1 and all randomized subjects**

Similar analyses than for PFS (BICR) in CPS  $\geq 10$ , 1 and in all randomized will be produced but using investigator assessment using primary definition.

##### **ORR (investigator) in CPS $\geq 10$ , 5, 1 and in all randomized subjects:**

Similar analyses than for Best Overall Response and ORR per BICR will be produced but using investigator assessment of response and progression.

##### **Duration of Response (BICR and investigator) in CPS $\geq 10$ , 5, 1 and all randomized subjects**

Duration of response (DoR) will be evaluated per BICR assessment and per investigator assessment. DoR will be estimated using the KM techniques. A two-sided 95% CI for median in each treatment group will be computed via the log-log transformation method. For the DoR analyses the population is restricted to subjects with measurable disease at baseline.

For DoR, type of event (PD, death) and status of subjects censored (received subsequent therapy, ongoing follow-up [current, non-current], off study [withdrew consent]) will be presented by treatment arm.

##### **Time to objective response (BICR) in randomized CPS $\geq 5$ subjects and all randomized subjects.**

Time to response will be evaluated per BICR assessment. Summary statistics will be provided for each treatment group for subjects who achieve PR or CR. For these analyses the population is restricted to subjects with measurable disease at baseline.

To assess further tumor response kinetics, time to response will be analyzed using the KM methodology. Kaplan-Meier curve will represent the cumulative rate of response over time. For

the non-responders, time to response will be censored at the maximum time of response + 1 day of all subjects in their respective treatment group. Cumulative Response Rates will be tabulated for Week 6, Week 12, Months 4, 6, 8, and 12, and overall Response Rate will be provided for each treatment group.

